6.5.2. Allowed Concomitant Therapy for IgAN Cohort

The allowed concomitant therapies for participants in the IgAN cohort will be consistent with standard of care and include the maximally tolerated dose of RAS-blocking agents, such as ACE inhibitors or ARBs.

The allowed concomitant treatment should be held stable throughout the Treatment Period of the study.

6.6. Additional Standard of Care Therapy for LN Cohort

Participants in the LN cohort will receive additional standard of care therapy in the event of a protocol-defined Renal Flare (Section 3.2) or Severe Extrarenal SLE Flare (Section 3.2.2).

Additional standard of care therapy is defined as intensification of current standard of care or introduction of new immunosuppressive therapies. After Week 26, additional standard of care therapy for participants with Suboptimal Response (Section 3.2.3) is allowed at the clinical discretion of the Investigator in conversation with the Medical Monitor.

The specific choice of additional standard of care therapy(ies) is generally at the discretion of the Investigator and may include approved medications for LN (eg, voclosporin, belimumab).

The following guidelines for corticosteroid dosing for protocol-defined Renal Flare and Severe Extrarenal SLE Flares should be considered to maintain treatment consistency:

- Participants with protocol-defined Renal Flare may be treated with prednisone up to 0.5 mg/kg/day (not to exceed 60 mg/day) for up to 2 weeks. Prednisone will then be tapered weekly to 10 mg/day within 6 weeks after the initial prednisone increase. Prednisone may further be tapered to \leq 7.5 mg/day at the discretion of the Investigator.
- Participants with Severe Extrarenal SLE flare may be treated with prednisone up to 1 mg/kg/day (not to exceed 60 mg/day) for up to 2 weeks. Prednisone will then be tapered every 2 weeks to achieve 7.5 mg/day within 12 weeks after the initial corticosteroid increase.
- Intravenous corticosteroids in equivalent doses may be allowed if gastrointestinal involvement temporality precludes oral corticosteroid use.

Prednisone \geq 10 mg for \leq 14 days will not be considered additional standard of care therapy in the following instances:

- Renal flares not meeting the protocol defined criteria for Renal Flare (see Section 3.2.1)
- Mild and non-severe Extrarenal SLE flares (see Section 3.2.2)
- Other medical conditions or surgery

The use of additional standard of care therapy should be discussed directly between the Investigator and Medical Monitor.

Additional standard of care therapy will be documented in the participant's CRF according to the CRF completion guidelines with the indication entered as "Renal Flare", "Severe Extrarenal SLE Flare", or "Suboptimal Response."

6.7. Concomitant Therapy

6.7.1. Allowed Medications and Therapies

Any medication or therapy (including over-the-counter or prescription medicines, vaccines, vitamins, and/or herbal supplements) deemed necessary for the participant's care during the study, or for the treatment of any AE, along with any other medications, other than those listed as disallowed medications in Section 6.7.2, may be given at the discretion of the Investigator. However, it is the responsibility of the Investigator to ensure that details regarding the medication are recorded on the CRF (Section 8.5.2).

If adequate blood pressure control is not achieved during the study, participants may receive additional antihypertensive agents, but not agents that affect proteinuria during the study. It is recommended that nonsteroidal anti-inflammatory drugs (NSAIDs) not be initiated during the study due to the possibility of adverse effects on renal function. They may be used, however, if necessary for the control of symptoms.

For participants in the LN cohort:

- Pneumocystis pneumonia prophylaxis is allowed at the discretion of the Investigator.
- Treatment with antimalarial agents such as hydroxychloroquine are strongly recommended unless contraindicated.
- Measures to prevent and treat osteoporosis are strongly encouraged during the study; these measures may include any, or all, of the following: calcium carbonate or citrate, Vitamin D, and bisphosphonates.
- Immunosuppressive drugs for additional standard of care therapy are allowed.

6.7.2. Disallowed Medications and Therapy

Participants in both cohorts are prohibited from receiving any of the following medications and therapies during the entire duration of study participation:

- Experimental interventions or therapies
- Eculizumab

- New use or modification of the dose of SGLT-2 inhibitors and direct renin antagonists
- New use or modification of the dose of RAS inhibitor treatment

In the event that a participant receives a prohibited medication and/or therapy, the participant should discontinue study drug (Section 7.1) with the exception of SGLT-2 inhibitors and direct renin antagonists (SGLT-2 inhibitors and direct renin antagonists are prohibited but may not require discontinuation of study drug based on the discussion and approval of the Investigator and Medical Monitor).

Participants in the IgAN cohort are also prohibited from receiving any of the following medications and therapies during the entire duration of study participation:

- Hydroxychloroquine
- Immunosuppressive agents (eg, MMF)
- Systemic corticosteroids for > 14 consecutive days (short-term steroid course for \leq 14 days for medical conditions not related to IgAN or surgery are permitted)

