During the Initial Evaluation Period, all participants will receive a weight-based loading dose of ravulizumab or placebo on Day 1, followed by maintenance doses of ravulizumab or placebo on Day 15 and then once every 8 weeks (q8w) thereafter. Loading and maintenance doses will be determined based on body weight (see table below). All participants will receive allowed

concomitant therapy consistent with the standard of care for participants with LN and IgAN throughout the study.

During the 24-week Extension Period, participants in the LN cohort will continue to receive their randomized allocation of study drug (ravulizumab or placebo) q8w. Participants in the LN cohort will receive additional standard of care therapy in the event of a protocol-defined Renal Flare or Severe Extrarenal systemic lupus erythematosus (SLE) Flare. Approved novel treatment(s) for LN is allowed. Additional standard of care therapy for participants with Suboptimal Response is allowed at the clinical discretion of the Investigator in conversation with the Medical Monitor. For the IgAN cohort, participants in the placebo group will receive a blinded loading dose of ravulizumab at Week 26 and participants in the ravulizumab group will receive a blinded ravulizumab dose of 900 mg at Week 26. Starting Week 28, all participants in the IgAN cohort will receive open-label weight-based doses of ravulizumab q8w until the end of the Extension Period.

During the 36-week Post-treatment Follow-up Period, all participants will continue to receive standard of care and will be monitored for safety, clinical events of interest, and kidney function. Participants who discontinue study drug early and agree to remain in the study should continue to attend their scheduled protocol visits until Week 50. During these visits, all assessments except for study drug administration should be performed according to the Schedule of Assessments. Participants who withdraw from the study will be followed for safety until 8 weeks after the last dose of study drug. The end of study is defined as the last participant's last visit in the Post-treatment Follow-up Period.

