To ensure the adequacy of the dose regimen, an interim pharmacokinetics (PK)/pharmacodynamics (PD) analysis for dose confirmation will be conducted by an independent clinical pharmacologist. The interim PK analysis will be conducted using masked PK/PD data from the first 10 participants treated with ravulizumab (a minimum of 3 participants in each disease-specific cohort). In the event of dose adjustments, the participants treated with the previous dose will switch over to the new dose and continue treatment on study but will be excluded from the primary efficacy analysis. Replacement participants may be enrolled to preserve study power.

Disclosure Statement: This is a parallel group treatment study with 2 disease cohorts of participants randomly assigned to 1 of 2 treatments that are participant, Investigator, and outcomes assessor blinded.

Number of Participants: Approximately 120 adult participants will be randomized. This will include approximately 60 participants in the LN cohort and approximately 60 participants in the IgAN cohort.

Intervention Groups and Duration:

Eligible participants will be enrolled into the study and will be randomized in a 2:1 ratio to receive either ravulizumab IV infusion or placebo IV infusion in combination with allowed concomitant therapy.

Ravulizumab will be supplied as a sterile, preservative-free 10 mg/mL solution in single-use vials, designed for administration via IV infusion by diluting into commercially available saline

(0.9% sodium chloride injection). Dosages will be based on the participant's body weight, as shown in the table below:

Body Weight Range (kg) ^a	Ravulizumab Loading Dose (mg)	Ravulizumab Maintenance Dose (mg)
≥ 40 to < 60	2400	3000
≥ 60 to < 100	2700	3900
≥ 100	3000	5400

a Dose regimen will be based on the last recorded study visit body weight. If the study drug is prepared the night before a visit, the weight from the most recent study visit should be used.

Placebo will have an identical appearance to that of ravulizumab.

For each participant, the total duration of study treatment (ravulizumab or placebo) will be up to 50 weeks and the total duration of study participation will be up to 86 weeks.

Data Monitoring Committee: No

Ethical Considerations and Benefit-Risk Assessment

[figure not shown]
This study will be conducted as specified in this protocol and in accordance with the following:

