During the Initial Evaluation Period, all participants will receive a weight-based loading dose of ravulizumab or placebo on Day 1, followed by weight-based maintenance doses of ravulizumab or placebo on Day 15 and then q8w thereafter ([Table 8](#)). All participants will receive allowed concomitant therapy consistent with the standard of care for participants with LN and IgAN throughout the study as defined in Section [6.5](#).

During the 24-week Extension Period, participants will continue to receive study drug (ravulizumab or placebo):

- Participants in the LN cohort will continue to receive their randomized allocation of study drug (ravulizumab or placebo) q8w until the end of the Extension Period. Participants will receive additional standard of care therapy in the event of a protocol-defined Renal Flare or Severe Extrarenal SLE Flare. Additional standard of care

therapy for participants with Suboptimal Response is allowed at the clinical discretion of the Investigator in conversation with the Medical Monitor.

- Participants in the IgAN cohort randomized to the placebo group will switch to receive a blinded loading dose of ravulizumab at Week 26 and then open-label weight-based dosing of ravulizumab q8w until the end of the Extension Period.
- Participants in the IgAN cohort randomized to the ravulizumab group will receive a blinded dose of 900 mg ravulizumab at Week 26 and then open-label weight-based dosing of ravulizumab q8w until the end of the Extension Period.

During the 36-week Post-treatment Follow-up Period, participants will continue to receive standard of care, at the discretion of the Investigator, and will be monitored for safety, clinical events of interest, and kidney function.

Participants who discontinue study drug early and agree to remain in the study should continue to attend their scheduled protocol visits until Week 50. During these visits, all assessments except for study drug administration should be performed according to the Schedule of Assessments.

Participants who withdraw from the study will be followed for safety until 8 weeks after the last dose of study drug.

The end of study is defined as the last participant's last visit in the Post-treatment Follow-up Period.

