7. DISCONTINUATION OF STUDY INTERVENTION AND PARTICIPANT DISCONTINUATION/WITHDRAWAL

7.1. Discontinuation of Study Drug

A participant has the right to discontinue study drug at any time.

Participants must permanently discontinue the study drug for any of the following reasons:

- Serious hypersensitivity reaction
- Severe uncontrolled infection
- Serious infusion reaction (such as bronchospasm with wheezing or requiring ventilator support or symptomatic hypotension, refer to Section 10.4) or serum sickness-like reactions manifesting 1 to 14 days after drug administration
- Use of disallowed medication as defined in Section 6.7.2
- Pregnancy or planned pregnancy
- Participant is unblinded during the Initial Evaluation Period

In addition, the study drug may be permanently discontinued for any of the following reasons:

- Adverse event that would, in the opinion of the Investigator, make continued participation in the study an unacceptable risk
- Deviation(s) from the protocol
- Significant non-compliance
- Alexion or the Investigator deems it is necessary for the participant
- Study termination

The reason for discontinuation of study drug will be recorded in the source documents and CRF.

If the study drug is definitively discontinued, every effort should be made to have the participant continue the study visits as per the SoA through Week 50/EoS. If a participant discontinues study drug due to an AE, including SAEs, the event should be followed as described in Section 10.3.3.

Participants who discontinue study drug and remain on study may receive treatment consistent with local standard practice for their disease per Investigator judgment, as applicable.

If the participant does not agree to continue with the study visits, the following activities should be completed:

- Early Discontinuation Visit should be performed as outlined in the SoA (Section 1.3).
- A Follow-up Phone Call will be performed 8 weeks following the participant's last dose of study drug to collect information on concomitant medications, nonpharmacological therapies and procedures, and AEs.

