8.5.2. Concomitant Medications and Procedures

Concomitant medications (including any medication, vitamin, herbal preparation or supplement) and procedures (defined in Section 6.7) are those received on or after the first study drug date (Day 1), including those started before Day 1 and continued after Day 1. At each study visit, participants should be questioned about any new medication or nondrug therapies or changes to concomitant medications and nondrug therapies since the last visit. Concomitant medications and nondrug therapies should be recorded in the source documents and the participant's CRF including:

- Reason for use
- Dates of administration including start and end dates
- Dosage information including dose and frequency

Any concomitant medication deemed necessary for the participant's care during the study, or for the treatment of any AE, along with any other medications, other than those listed as disallowed medications in Section 6.7.2, may be given at the discretion of the Investigator. However, it is the responsibility of the Investigator to ensure that details regarding all medications are recorded in full, in the participant's source documents and CRF.

Information regarding the use of disease-specific treatment received during the course of the study will be recorded in the source documents and the participant's CRF, including:

- For participants in the LN Cohort:
 - Additional standard of care therapy (Section 6.6) for protocol-defined Renal Flare, Severe Extrarenal SLE Flare, or Suboptimal Response
 - Treatment(s) for non-severe extrarenal SLE flare or other renal flare not defined in protocol

Vaccination and antibiotics administered for prophylaxis of meningococcal infection (if applicable) will also be recorded.

The Medical Monitor should be contacted if there are any questions regarding concomitant medications or procedures.

Allowed concomitant therapy and corticosteroid tapering for participants with LN is discussed in Section 6.5.1 and allowed concomitant therapy for participants with IgAN is discuss in Section 6.5.2.

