8.13. Post-treatment Follow-up Period

During the 36-week Post-treatment Follow-up Period, participants will continue to receive standard of care and will be monitored for clinical events of interest and kidney function.

All participants will be followed for safety until 8 weeks after the participant's last dose of study drug to collect information on concomitant medications, nonpharmacological therapies and procedures, and AEs. The final safety evaluation for participants in the LN will occur at the Week 50 Visit and participants in the IgAN cohort will have a Follow-up Phone Call performed at Week 52.

Participants are not required to come into the clinic for the Post-treatment Follow-up Period visits. At each Post-treatment Follow-up Visit through Week 86, the information described below will be documented in the participant's CRF for the 12-week period since the previous study visit.

For participants in both cohorts, the following laboratory results will be documented:

- Record the UPCR results from the participant's most recent standard of care testing conducted by local laboratory. Spot urine studies may be used; a morning void is preferred.
- Record serum creatinine results from the participant's most recent standard of care testing conducted by local laboratory.

For participants in the LN cohort, information will include, but is not limited to:

- In the Investigator's opinion, did the patient experience a renal flare or extrarenal flare
- Documentation of any changes in immunosuppression therapy (intensified, new agent, or change in dose)
- Progression of kidney disease including dialysis and kidney transplant

For participants in the IgAN cohort, information will include, but is not limited to:

- Progression of kidney disease including dialysis and kidney transplant
- Documentation of any changes in immunosuppressive therapy (new agent or change in dose)
- Documentation of any changes in alternative therapy (new agent or change in dose)

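### Protocol 6.7.2 bans disease treatments until the end of participation (up to 86 weeks) with no off-drug exception, in conflict with 7.1, 4.1, 8.13 and, for IgAN RAS inhibitors, 6.5.2

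*Protocol*

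**What the plan says.** Protocol 6.7.2 has two lists, each with the same duration. The list for both cohorts covers experimental therapies, eculizumab, new use or dose change of SGLT-2 inhibitors and direct renin antagonists, and new use or dose change of RAS inhibitors. The IgAN list adds hydroxychloroquine, immunosuppressive agents and systemic steroids for more than 14 consecutive days: "Participants in the IgAN cohort are also prohibited from receiving any of the following medications and therapies during the entire duration of study participation". The Synopsis (1.1) separates up to 50 weeks of treatment from participation: "the total duration of study participation will be up to 86 weeks".

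The only exception in 6.7.2 is that SGLT-2 inhibitor or direct renin antagonist use need not lead to stopping study drug. Nothing addresses participants who are already off it.

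Other sections set different terms:
- 7.1: "Participants who discontinue study drug and remain on study may receive treatment consistent with local standard practice for their disease per Investigator judgment".
- 1.1, on the 36-week follow-up: "all participants will continue to receive standard of care and will be monitored for safety, clinical events of interest, and kidney function". Section 4.1 adds discretion: "participants will continue to receive standard of care, at the discretion of the Investigator".
- 8.13, on what is recorded for IgAN in follow-up: "Documentation of any changes in immunosuppressive therapy (new agent or change in dose". Changes in alternative therapy are recorded as well.
- 6.5.2: IgAN background therapy (RAS blockers) is to be kept stable through the Treatment Period, which 6.9 ends with the Extension Period.
- 8.5.2, on Investigator discretion: "along with any other medications, other than those listed as disallowed medications in Section 6.7.2, may be given at the discretion of the Investigator". Section 6.7.1 says the same, and on blood pressure adds that "participants may receive additional antihypertensive agents, but not agents that affect proteinuria during the study".

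**The concern.** A ban on treatments that could confound proteinuria makes sense while study drug is given. Here it lasts for all of participation, so it covers people who have stopped drug early and people who have finished treatment and are only being followed. Other sections tell sites that these same people may have standard treatment.

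Two things are at stake. The first is care and consistent conduct: a site that reads 6.7.2 literally could withhold a RAS inhibitor change or an immunosuppressant from an off-drug IgAN participant, while a site that follows 7.1, 4.1 and 8.13 would give it. The second is the deviation count: item 3 of the programmatic check in SAP 6.2.4 flags receipt of any disallowed treatment without a time window, so care allowed by 7.1 could be counted as a deviation.

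**Working it through.** **Length of the ban.** Inputs are the stated periods (4.1) and the nominal visit days in the Schedule of Activities.
- Participation: 26 + 24 + 36 = 86 weeks, which reproduces the stated figure. Screening (up to 6 weeks) is not included. Treatment: 26 + 24 = 50 weeks.
- Completers, after Week 50: (603 − 351)/7 = 252/7 = 36 weeks, and 36/86 = 42% of participation.
- IgAN completers, from the last dose on Day 309: (603 − 309)/7 = 294/7 = 42 weeks.
- Early IgAN stoppers followed to Week 50, from last dose. Scheduled doses fall on Days 1, 15, 71, 127, 183, 197, 253 and 309. Last dose Day 1: (351 − 1)/7 = 50 weeks. Last dose Day 127: (351 − 127)/7 = 32 weeks. Last dose Day 253: (351 − 253)/7 = 14 weeks. The range is about 14 to 50 weeks. It is approximate because the clock starts at the last dose given, not at the first dose missed.

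**Which bans conflict.** For IgAN there are 4 common + 3 IgAN-only = 7 bullets.

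| Bullet in 6.7.2 | Set against | Result |
|---|---|---|
| RAS inhibitor changes, IgAN | 6.5.2 asks for stability only to the end of the Treatment Period | Clear: two windows for the same drugs |
| Immunosuppressive agents, IgAN | 8.13 expects and records new agents in follow-up | Clear |
| Steroids > 14 days; hydroxychloroquine; SGLT-2 inhibitors and direct renin antagonists, IgAN | 7.1 and 4.1 | Conflict only if local standard practice |
| RAS inhibitors; SGLT-2 inhibitors and direct renin antagonists, LN | 7.1 and 4.1 | Conflict only if local standard practice |
| Experimental therapies; eculizumab | None | Not in dispute |

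IgAN: 2 clear + 3 conditional + 2 not in dispute = 7. LN: 0 clear + 2 conditional + 2 not in dispute = 4.

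**Whether the text resolves itself.** Section 6.7.2 cites 7.1 only for stopping study drug, not as an exception. Sections 6.7.1 and 8.5.2 place Investigator discretion under 6.7.2, not above it. Section 8 disallows waivers, although in the context of study procedures. The rules can also loop: an IgAN participant given an immunosuppressant should stop study drug and is urged to keep attending; 7.1 then allows treatment of the disease, while 6.7.2 still bans the drug that led to the stop.

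**Effect on the analysis.** The primary endpoint is at Week 26, and SAP 5.3.2 imputes data on or after treatment discontinuation, so off-drug care does not enter the primary analysis. Per-Protocol Set item 7 (SAP 4) is limited to the 26-week Initial Evaluation Period. Off-drug values are used in the supplementary treatment policy analysis (SAP 5.3.4), where uneven site practice could have some effect.

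**The case against.** The best defence is that the intent is plain. Section 7.1 is the specific rule for people who stop drug and stay on study. The only consequence 6.7.2 states is stopping study drug, which means nothing once drug has stopped. Section 6.5.2 shows the intended window for RAS blockers, 8.13 names new agents in IgAN follow-up, and 8.5.2 sends questions about concomitant medication to the Medical Monitor. A site that withheld care would have to pass over all of these. On the SAP side, 6.2.4 is a completeness check, deviations are determined under an SOP and graded as important or not, and item 3 does not define what counts as disallowed.

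Much of this stands. It shows the likely intent and keeps the severity down. It also rules out a stronger reading, that completers have nothing beyond general standard-of-care wording on their side: 6.5.2 speaks to RAS inhibitors and 8.13 to immunosuppressants.

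It does not remove the conflict. Section 7.1 is worded for those who discontinue, not for those who complete. Discretion is made subject to 6.7.2 in two places. Section 6.5.2 sets a shorter window without amending the longer one, and recording a new agent is not the same as permitting it. Case-by-case calls to the Medical Monitor do not ensure that sites act alike.

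**Conclusion.** The point holds as a conflict between stated rules, of minor to moderate severity. The off-drug time under the ban is 36 weeks after Week 50 for completers (42 weeks from the last IgAN dose) and about 14 to 50 weeks from last dose for early IgAN stoppers followed to Week 50. Two IgAN bans are clearly affected. The remaining disease-treatment bans, and LN as a whole, are affected only where the change is local standard practice, which the documents do not describe.

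A reader might infer more, and the documents do not support it:
- That participants will be denied care, or that a number harmed can be given. The plan states no rate of need for these drugs, and several sections point sites towards treating.
- That every listed ban is at fault. The eculizumab and experimental-therapy bans can reasonably run throughout. Prolonged steroids are not a clear case either: exclusion criterion 26 shows that such treatment is used in IgAN, but 2.3.2 calls the evidence on immunosuppression inconclusive.
- That the primary result is at risk. It is not.

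The figures assume nominal visit days and the wording of the current protocol and SAP.

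**What to change.** - **Protocol 6.7.2:** limit the disease-treatment bullets to the Treatment Period while the participant is on study drug. These are RAS inhibitor, SGLT-2 inhibitor and direct renin antagonist changes in both cohorts, and hydroxychloroquine, immunosuppressants and steroids for more than 14 days in IgAN. Cross-refer to 7.1 and 8.13 for participants off drug. Keep the eculizumab and experimental-therapy bans for all of participation.
- **Protocol 6.7.1:** put the same limit on the sentence that restricts added antihypertensives.
- **SAP 6.2.4 item 3:** apply the same window. Leave Per-Protocol Set item 7 as it is.

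The cost is a short protocol amendment, with IRB/IEC approval if it is classed as substantial (10.1.1), and one line in the SAP. It needs no new data and leaves sample size, power and the primary analysis unchanged.
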